4.2.6 Safety Analysis

Safety will be evaluated by the collection and analysis of data on (S)AEs. All (S)AEs will be reported, regardless of their relationship to study product (*Table 24 in Section 7.1*). The number of subjects with adverse events and the number of adverse events will be reported by body system and by treatment arm (*Table 24A-B in Section 7.1*). (S)AEs results (the number of subjects with adverse event and the number of adverse events) will be compared by treatment arm, with statistical tests for differences in proportion of subjects with serious adverse events between study arms. These analyses will use the ITT population and two-sided tests with significance level of 0.05 (*Table 25A in Section 7.1*).

Missing Data: Initially we will assess the extent and pattern of missing data using frequencies and cross-tabulations. If data are missing for only a few cases (5% or less), then data analysis will be conducted only on study participants with complete data. However, when such a strategy would result in loss of data from a substantial proportion of participants (i.e., 20%) or would lead to biased or inaccurate results, then sensitivity analysis or some form of imputation will be performed. The form of

imputation used will depend on the nature of the data that are missing. If data are missing for primary endpoint (treatment failure), frequencies for missing data by center, patient characteristic (clinical and demographic), and medication used will be examined. If there are significant associations of missingness with any of these characteristics, we would consider intent-to treat analysis with imputation methods such as regression technique, hot-deck, or best/worst case (for binary outcomes) and choose the one that would be most appropriate for type of missing data pattern (missing at random). If there is partial follow-up, that partial data might allow us to do an imputation. The imputation will be employed if there is a clear evidence of bias due to missing data. Sensitivity analyses will be performed to assess how sensitive results are to reasonable changes in the assumptions that are made for missing data.

To be considered evaluable a child must meet (a) below and one of (b) , (c) or (d):

(a) have taken study medication, AND;

(b) complete the Test of Cure visit, OR;

(c) have prior evidence of a treatment failure;

(d) answered YES to OS #3 (The Off Study CRF Question #3 is “Was a Test of Cure visit completed (or an interim visit if the subject was symptomatic prior to Test of Cure)?”).

5. Planned Outputs

5.1 Tables

▪ Definition of populations

- **Population 1:** All subjects taking at least one dose of study treatment between Day 6 and Day 10 who have been evaluated for treatment success at TOC or have failed prior to TOC (ITT population)
- **Population 2:** The enrolled subjects who were adherent to their assigned study regimen and completed more than 80% of the prescribed dose between Day 6 and Day 10 (per-protocol population)
- **Population 3:** Subjects in population 2 who did not experience a treatment failure.
- **Population 4:** Subjects in population 2 who have a stool sample at TOC visit. Some treatment failures will not have a sample collected at TOC because they failed prior to TOC. Treatment failures without the sample at TOC would be excluded from population 4.

▪ Definition for a subject having primary endpoint

The primary endpoint of this study is the proportion of children experiencing treatment failure (symptomatic UTI) at the TOC visit (Day 11-14).

▪ Data handling

- Treat blanks and “.” as missing unless specified otherwise.

6. References

1. [name] R, Chan E. A meta-analysis of randomized, controlled trials comparing short- and long-course antibiotic therapy for urinary tract infections in children. *Pediatrics*. May 2002; 109(5):E70-70.

7. Appendices

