7.5 Assessment of Subject Compliance with Study Intervention/Study product

At the Enrollment Visit, the parent(s) or guardian(s) will be given a subject medication diary. The Study Nurse/Nurse Practitioner/Physician will document the study product kit number, the date of the enrollment visit, and the date the study product was started. The Study Nurse/Nurse Practitioner/Physician will also explain the study product dosage instructions to the child’s caregiver(s): after completing five days of the originally prescribed antibiotic to then take the study product for five additional days (days six – ten). The Study Nurse/Nurse Practitioner/Physician will also explain how to use the medication diary to report the daily dose, the date, the time the study product was taken and the date that the study product was stopped. The Study Nurse/Nurse Practitioner/Physician will also explain how important it is to adhere to the instructions to complete the first five days of the originally prescribed antibiotic and then on days six – 10 to take the study product. The Study Nurse/Nurse Practitioner/Physician will collect the subject’s medication diary and study product bottle at the Test of Cure Post-Treatment Visit on Day 11 - 14.

Dose Adjustments/Modifications/Delays

Subject families will be told that if the child has missed one dose of antibiotic, they should not double the next dose. Instead, they should take the missed dose as prescribed as soon as they remember. At the Enrollment Visit, the Study Nurse/Nurse Practitioner/Physician will provide the child’s parent(s)/legal guardian(s) with a study medication diary to record the day, time, and dose taken, missed doses, reason dose was missed (e.g. forgot to take dose, vomiting after taking study product) to help them to help with adherence and compliance.

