Primary Analysis / Efficacy Analysis: The primary analysis will follow Intent-to-Treat (ITT) principles, with subjects analyzed according to randomized treatment assignment. In addition, a “per-protocol” analysis will be performed; the per-protocol analysis would include only subjects who were adherent to their assigned study regimen and completed 80% or more of the prescribed dose. All subjects taking at least one dose of study drug(s) who have been evaluated for treatment success at TOC visit or have failed treatment prior to TOC will be included in the ITT analysis (see the table below). The primary analysis will be a non-inferiority test comparing the number of symptomatic UTIs at the TOC visit between two treatment arms along with the 5% equivalence interval. The confidence interval of the difference in symptomatic UTI rates between the short-course and standard-of-care therapies will be calculated to evaluate whether this difference is less than or equal to the equivalence interval. This will be a one-sided test with $\alpha = 0.05$. Subjects with asymptomatic bacteriuria or who are asymptomatic with a

positive culture including pyuria will NOT be considered treatment failures for the primary outcome measure.

Table 9: SCOUT Study product Dosage Adherence

Antibiotic Drug	Antibiotic Dosage	80% of Expected Doses
Trimethoprim-Sulfamethoxazole (TMP-SMX)	8 mg/kg/day of Trimethoprim in 2 divided doses, Max 160mg BID Trimethoprim	Eight doses
Amoxicillin-Clavulanate*	45 mg/kg/day in 2 divided doses, Max 875 mg Q12H	Eight doses
Cefixime	8 mg/kg/day in 1 dose, Max 400 mg	Four doses
Cephalexin	50mg/kg/day in 3 divided doses	Twelve Doses

*Amoxicillin-clavulanate is no longer included as a study antibiotic, but subjects randomized to this treatment prior to its removal must have taken at least eight doses to be included in the per-protocol analysis.

Secondary Analysis:

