4.2.2 Primary/Efficacy analysis

The primary endpoint of this study is the proportion of children experiencing treatment failure (symptomatic UTI) at the TOC visit (Day 11-14).

The primary analysis will follow intent-to-treat (ITT) principles, with subjects analyzed according to randomized treatment assignment (*Table 3 in Section 7.1*). In addition, a “per-protocol” analysis will be performed; the per-protocol analysis would include only subjects who were adherent to their assigned study regimen and completed more than 80% of the prescribed dose (*Table 4 in Section 7.1*). All subjects taking at least one dose of study treatment between Day 6 and Day 10 who have been evaluated for treatment success at TOC visit or have failed before TOC will be included in the ITT analysis (See Table 4 below).

The primary analysis will be a non-inferiority test comparing the proportion of children with symptomatic UTIs at the TOC visit between two treatment arms to evaluate whether the difference is within the 5% equivalence interval. This test will be conducted by calculating the one-sided 95% upper confidence limit for the difference in symptomatic UTI (treatment failure) rates between the short-course and standard-of-care therapies. If this limit is less than or equal to the equivalence interval (0.05), then we will conclude that short course therapy is not inferior to standard therapy. Subjects with asymptomatic bacteriuria or who are asymptomatic with a positive culture including pyuria will NOT be considered treatment failures for the primary outcome measure.

Table 4: SCOUT Study Medication Dosage Adherence

Antibiotic Drug	Antibiotic Dosage	80% of Expected Doses
Trimethoprim-Sulfamethoxazole (TMP-SMX)	8 mg/kg/day of Trimethoprim in 2 divided doses, Max 160mg BID Trimethoprim	Eight doses
Amoxicillin-Clavulanate	45 mg/kg/day in 2 divided doses, Max 875 mg Q12H	Eight doses
Cefixime	8 mg/kg/day in 1 dose, Max 400 mg	Four doses
Cephalexin	50mg/kg/day in 3 divided doses	Twelve Doses

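### The SAP requires more than 80% of doses for the per-protocol set where the protocol requires 80% or more, so as written one missed cefixime dose excludes a child

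*SAP*

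**What the plan says.** Protocol 12.4 defines the per-protocol set as children who were "adherent to their assigned study regimen and completed 80% or more of the prescribed dose". Its Table 9 has a column headed "80% of Expected Doses" that lists 8 doses for TMP-SMX, 8 for amoxicillin-clavulanate, 4 for cefixime and 12 for cephalexin. A footnote on amoxicillin-clavulanate, since withdrawn as a study drug, says that children randomized to it "must have taken at least eight doses to be included in the per-protocol analysis".

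The SAP states the rule twice and differently. Section 4.2.2 requires children to be "adherent to their assigned study regimen and completed more than 80% of the prescribed dose". Section 5.1 defines Population 2 as those who "completed more than 80% of the prescribed dose between Day 6 and Day 10 (per-protocol population"). Yet SAP Table 4 prints the same counts as the protocol: 8, 8, 4 and 12.

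**The concern.** One document includes the child at exactly 80% and the other excludes that child. With so few doses, exactly 80% is a common place to land, above all for the once-daily drug.

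The strict wording also sets a different real standard for each drug, which neither document states or justifies. Cefixime and cefdinir are two of the four antibiotic strata in Protocol 6.4.1. Children in those strata would need perfect adherence, while the others may miss a dose or two. That changes the antibiotic mix of the per-protocol comparison and discards children who met the protocol's rule.

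Population 2 is widely used. It is the set for the per-protocol table of the primary endpoint (shell Table 4), and Populations 3 and 4 are drawn from it. The shells for the secondary endpoints (Tables 5-11), the subgroup comparisons (Tables 12-17) and the secondary regression models (Tables 19-23) all name Population 2, 3 or 4.

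There is also a link to outcome. Under Protocol 6.4.4 and 8.2, a child with a confirmed symptomatic UTI during Days 6-10 stops study product. If adherence is counted against the full five-day course, a cefixime child who fails after four doses is kept under the protocol and dropped under the SAP. The cut-off would then remove a treatment failure from a non-inferiority comparison.

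**Working it through.** **Inputs**

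- Duration: families are told to "take the study product for five additional days (days six – ten"), which is 5 days (Protocol 7.5).
- Cefixime: "8 mg/kg/day in 1 dose, Max 400 mg", one dose a day (SAP Table 4).
- TMP-SMX: "8 mg/kg/day of Trimethoprim in 2 divided doses, Max 160mg BID Trimethoprim", two doses a day (SAP Table 4). Amoxicillin-clavulanate is also twice daily.
- Cephalexin: three doses a day (SAP Table 4).
- Children first prescribed cefdinir take cefixime or its placebo (Protocol 7.2), so the cefixime count applies to them.

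**Step 1: reproduce the tabulated counts.** Expected doses = doses per day × 5. The tabulated count should be 0.8 × expected doses.

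- Twice-daily drugs: 0.8 × 10 = 8
- Cefixime: 0.8 × 5 = 4
- Cephalexin: 0.8 × 15 = 12

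All printed counts are reproduced, and each is exactly 80%. A child at the tabulated count passes an inclusive rule and fails a strict one.

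**Step 2: smallest whole number of doses that qualifies**

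| Drug | Expected | Protocol (80% or more) | SAP (more than 80%) | Effective SAP cut-off |
|---|---|---|---|---|
| TMP-SMX, amoxicillin-clavulanate | 10 | 8 | 9 | 9/10 = 90% |
| Cefixime (including cefdinir children) | 5 | 4 | 5 | 5/5 = 100% |
| Cephalexin | 15 | 12 | 13 | 13/15 = 86.7% |

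**Step 3: how many children fall between the two rules.** The documents give no rate of missed doses, so this is an illustration. Assume each dose is missed independently with probability q. The share at exactly 80% is C(n, m) × (1 − q)^(n − m) × q^m, where n is the expected doses and m the number missed (2 of 10, 1 of 5 or 3 of 15). At q = 5%:

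- Twice-daily: 45 × 0.95^8 × 0.05^2 = 0.075
- Cefixime: 5 × 0.95^4 × 0.05 = 0.204
- Cephalexin: 455 × 0.95^12 × 0.05^3 = 0.031

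| Miss rate per dose | Cefixime/cefdinir | Twice-daily drugs | Cephalexin |
|---|---|---|---|
| 2% | 9.2% | 1.5% | 0.3% |
| 5% | 20.4% | 7.5% | 3.1% |
| 10% | 32.8% | 19.4% | 12.9% |

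**Step 4: relax independence.** Missed doses may cluster within a child. Under a beta-binomial model with an assumed within-child correlation of 0.2, the cefixime shares become 4.7%, 10.7% and 18.2% at miss rates of 2%, 5% and 10%. With a correlation of 0.3 and a 5% miss rate, the cefixime share is 8%.

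**The case against.** The strongest reply is that the trial's main conclusion does not depend on this wording. The primary analysis is ITT, which needs only one dose of study product, and the per-protocol analysis is an addition. Neither document requires the two sets to agree before non-inferiority is declared. This stands, and it limits the reach of the problem to the per-protocol, secondary and subgroup results.

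Second, no bias between arms has been shown. Randomization is stratified by antibiotic, the trial is double-blind and placebo follows the same schedule, so either cut-off asks for the same dose count in both arms within each drug. This largely stands. What is shown is a change in who is analysed and in the drug mix, not a shift in the treatment difference. The possible exclusion of failures who stop early is a route to such a shift, but its size cannot be computed from the documents.

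Third, SAP Table 4 only lists counts and does not say that reaching them is enough. The protocol's explicit footnote concerns a drug no longer in use. Both points are correct, but the protocol's main sentence is general and inclusive, and counts of exactly 80% cannot be minimum values under a strict rule.

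Fourth, the percentages rest on assumptions. Clustering roughly halves the cefixime figures, and families are told to give a missed dose when they remember it (Protocol 7.5), so a late dose may still count as taken. The documents do not give the antibiotic mix, so the total loss from Population 2 cannot be calculated. All of this is fair. It affects the size of the problem, not the contradiction.

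**Conclusion.** The concern holds. The SAP text contradicts the protocol on who belongs to the per-protocol set and does not fit the SAP's own dose table. No other text reconciles them. The differences of one whole dose per drug in Step 2 are exact and need no assumption. The shares of children affected are illustrative. On cefixime, for miss rates of 2% to 10%, they run from about 9% to 33% if misses are independent and from about 5% to 18% with a within-child correlation of 0.2. The ITT result for the primary endpoint does not change. The rule should be settled before unblinding; otherwise a programmer, or someone who has seen the results, will choose the denominator for most efficacy tables.

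**What to change.** In SAP 4.2.2 and in the Population 2 definition in SAP 5.1, replace the strict cut-off with 80% or more of the Day 6-10 doses. State the minimum counts there: at least 8 of 10 for TMP-SMX and amoxicillin-clavulanate, at least 4 of 5 for cefixime (including children first prescribed cefdinir), and at least 12 of 15 for cephalexin. This matches Protocol 12.4 and the counts in both dose tables. Populations 3 and 4 then follow without further editing.

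The cost is two wording changes in the SAP before unblinding. No new data are needed, and no dosing or clinical rule changes.

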7.1 SAP Table shells

Table 1. Randomization review

	Arm 1: Standard Course Total= xxx N (%)	Arm 2: Short Course Total= xxx N (%)
Presence of fever		
Yes		
No		
Antibiotic Type		
TMP-SMX		
Amoxicillin-Clavulanate		
Cefixime		
Cefdinir		
Cephalexin		

Note: Chi-square tests for frequencies across two treatment groups

1. P=0.xxxx for Presence of fever versus No fever
2. P=0.xxxx for Antibiotic Type

Table 2. Demographic and baseline data

	Arm 1: Standard Course Total= xxx N (%)	Arm 2: Short Course Total= xxx N (%)	p-value
Age, Mean ± SD			
2 months -35 months			
3 – 6 years			
7 – 10 years			
Gender			
Male			
Female			
Race/ethnicity			
White			
Black/African American			
Asian			
Native Hawaiian/Other Pacific Islander			
American Indian/Alaska Native			
Multi-Racial			
Other			
Hispanic			
Yes			
No			

Table 2 Specifications

- Repeat the analysis on population 1 (ITT population) and 2 (per-protocol population) separately as Table 2a and 2b.
- Table 2 was designed to show the frequencies and column percentage of subjects within each category unless was specified as to show means and standard deviation. Some categorical variables may need to be created based on numeric values.

Table 3. Comparison of the proportion of subjects with symptomatic UTIs prior to or at the TOC visit for ITT population (Population 1) (Primary analysis)

	Arm 1: Standard Course Total= xxx N (%)	Arm 2: Short Course Total= xxx N (%)	Difference of proportion and one- sided 95% confidence limit
Treatment Failure			

SAS note: Using RISKDIFF ALPHA=0.10 in the TABLE STATEMENT of PROC FREQ procedures to calculate the difference of proportion and one sided 95% CI

Table 4. Comparison of the proportion of subjects with symptomatic UTIs prior to or at the TOC visit for per protocol population (Population 2) (Primary analysis)

	Arm 1: Standard Course Total= xxx N (%)	Arm 2: Short Course Total= xxx N (%)	Difference of proportion and one- sided 95% confidence limit
Treatment Failure			

Table 5. Comparison of the proportion of subjects with a recurrent infection at any time after the TOC visit for per protocol population (Population 3) (Secondary analysis, Endpoint a)

	Arm 1: Standard Course Total= xxx N (%)	Arm 2: Short Course Total= xxx N (%)	Difference of proportion and two- sided 95% confidence limit
Recurrent Infection			

Table 6. Comparison of the proportion of subjects with asymptomatic bacteriuria at the TOC visit for per protocol population (Population 2) (Secondary analysis, Endpoint b)

	Arm 1: Standard Course Total= xxx N (%)	Arm 2: Short Course Total= xxx N (%)	Difference of proportion and two- sided 95% confidence limit
Asymptomatic Bacteriuria			

Table 7. Comparison of the proportion of subjects with clinical symptoms that may be related to a UTI prior to or at the TOC visit for per protocol population (Population 2) (Secondary analysis, Endpoint d)

	Arm 1: Standard Course Total= xxx N (%)	Arm 2: Short Course Total= xxx N (%)	Difference of proportion and two- sided 95% confidence limit
Clinical Symptoms			

Table 8. Comparison of the proportion of subjects with positive urine cultures prior to or at the TOC visit for per protocol population (Population 2) (Secondary analysis, Endpoint e)

	Arm 1: Standard Course Total= xxx N (%)	Arm 2: Short Course Total= xxx N (%)	Difference of proportion and two- sided 95% confidence limit
Positive Urine Cultures			

Table 9: Comparison of the proportion of children that develop the gastrointestinal colonization of antimicrobial resistant E. coli and K. pneumoniae through Outcome assessment visit (Day 24-30) for per protocol population (Population 2) (Secondary analysis, Endpoint c)

	Arm 1: Standard Course Total= xxx N (%)	Arm 2: Short Course Total= xxx N (%)	p -value for Chi- square test
Enrollment visit (Day 2-6)			
Any antibiotic-resistant E. coli Any antibiotic-resistant K. pneumoniae Any antibiotic resistance Both antibiotic-resistant E. coli and antibiotic-resistant K. pneumoniae Multiple antibiotic-resistant E. coli Multiple antibiotic-resistant K. pneumoniae			
TOC visit (Day 11-14)			
Any antibiotic-resistant E. coli Any antibiotic-resistant K. pneumoniae Any antibiotic resistance Both antibiotic-resistant E. coli and antibiotic-resistant K. pneumoniae Multiple antibiotic resistance to E. coli Multiple antibiotic resistance to K. pneumoniae			
Outcome assessment visit (Day 24-30)			
Any antibiotic-resistant E. coli Any antibiotic-resistant K. pneumoniae Any antibiotic resistance Both antibiotic-resistant E. coli and antibiotic-resistant K. pneumoniae Multiple antibiotic resistance to E. coli Multiple antibiotic resistance to K. pneumoniae			

Table 10: Comparison of the proportion of children that develop emergent gastrointestinal colonization of antimicrobial resistant E. coli or K.pneumoniae through outcome assessment visit (day 24-30) for per protocol population (Population 4) (Secondary analysis c)

	Arm 1: Standard Course Total= xxx N (%)	Arm 2: Short Course Total= xxx N (%)	p-value for Chi-square test
TOC visit (Day 11-14)			
Outcome assessment visit (Day 24-30)			

Table 11: Comparison of the proportion of children that develop emergent gastrointestinal colonization of antimicrobial resistant E. coli or K.pneumoniae by resistant agent through outcome assessment visit (day 24-30) for per protocol population (Population 4) (Secondary analysis c)

	Arm 1: Standard Course Total= xxx N (%)	Arm 2: Short Course Total= xxx N (%)	p-value for Chi-square test
TOC visit (Day 11-14)			
Emergent Resistance to TMP-SMX			
Emergent Resistance to Amoxicillin-clavulanate			
Emergent Resistance to Ceftazi-dime			
Emergent Resitance to Ampicillin			
Outcome assessment visit (Day 24-30)			
Emergent Resistance to TMP-SMX			
Emergent Resistance to Amoxicillin-clavulanate			
Emergent Resistance to Ceftazi-dime			
Emergent Resitance to Ampicillin			

Table 12. Comparison of the proportion of subjects with symptomatic UTIs prior to or at the TOC visit for subpopulations (Population 2) (Primary endpoint)

	Arm 1: Standard Course Total= xxx N (%)	Arm 2: Short Course Total= xxx N (%)	p-value for Chi-square test
Age Group 2 month – 35 months 3 – 6 years 7-10 years			
Febrile Febrile UTI Non-Febrile UTI			
Antibiotic Type TMP-SMX Amoxicillin-Clavulanate Cefixime Cefdinir Cephalexin			
Site CHOP PITT			

Table 13. Comparison of the proportion of subjects with a recurrent infection at any time after the TOC visit for subpopulations (Population 3) (Secondary endpoint a)

	Arm 1: Standard Course Total= xxx N (%)	Arm 2: Short Course Total= xxx N (%)	p-value for Chi-square test
Age Group 2 month – 35 months 3 – 6 years 7-10 years			
Febrile Febrile UTI Non-Febrile UTI			
Antibiotic Type TMP-SMX Amoxicillin-Clavulanate Cefixime Cefdinir Cephalexin			
Site CHOP PITT			

Table 14. Comparison of the proportion of subjects with asymptomatic bacteriuria at the TOC visit for subpopulation (Population 2) (Secondary endpoint b)

	Arm 1: Standard Course Total= xxx N (%)	Arm 2: Short Course Total= xxx N (%)	p-value for Chi-square test
Age Group 2 month – 35 months 3 – 6 years 7-10 years			
Febrile Febrile UTI Non-Febrile UTI			
Antibiotic Type TMP-SMX Amoxicillin-Clavulanate Cefixime Cefdinir Cephalexin			
Site CHOP PITT			

Table 15. Comparison of the proportion of subjects with clinical symptoms that may be related to a UTI prior to or at the TOC visit for subpopulation (Population 2) (Secondary endpoint d)

	Arm 1: Standard Course Total= xxx N (%)	Arm 2: Short Course Total= xxx N (%)	p-value for Chi-square test
Age Group 2 month – 35 months 3 – 6 years 7-10 years			
Febrile Febrile UTI Non-Febrile UTI			
Antibiotic Type TMP-SMX Amoxicillin-Clavulanate Cefixime Cefdinir Cephalexin			
Site CHOP PITT			

Table 16. Comparison of the proportion of subjects with positive urine cultures prior to or at the TOC visit for subpopulation (Population 2) (Secondary endpoint e)

	Arm 1: Standard Course Total= xxx N (%)	Arm 2: Short Course Total= xxx N (%)	p-value for Chi-square test
Age Group 2 month – 35 months 3 – 6 years 7-10 years			
Febrile Febrile UTI Non-Febrile UTI			
Antibiotic Type TMP-SMX Amoxicillin-Clavulanate Cefixime Cefdinir Cephalexin			
Site CHOP PITT			

Table 17. Comparison of Risk of emergent colonization with antimicrobial resistant E. coli or K. pneumoniae in Gastrointestinal Tract for Subpopulations (Population 4) (Secondary endpoint c)

	Arm 1: Standard Course Total= xxx N (%)		Arm 2: Short Course Total= xxx N (%)		p- value 1	p- value 2
	TOC visit	Outcome visit	TOC visit	Outcome visit		
Age Group						
2 – 35 months						
3 – 6 years						
7-10 years						
Febrile						
Febrile UTI						
Non-Febrile UTI						
Antibiotic Type						
TMP-SMX						
Amoxicillin- Clavulanate						
Cefixime						
Cefdinir						
Cephalexin						
Site						
CHOP						
PITT						

p-value 1 and p-value 2 will reported from Chi-square test comparing the proportions between sub-populations and treatment arms at TOC visit, and Outcome assessment visit, respectively.

Table 18. Multivariable Logistic Regression Analysis for Treatment failure (Symptomatic UTI at TOC visit) (Population 1) (Primary endpoint)

	Odds ratio	95% CI	p -value
Arm 1 Standard Course(reference)			
Arm 2 Short Course			
Covariates			

Interaction Term			

CI: Confidence Interval

SAS tips: SCALE=NONE in the MODEL statement of the PROC LOGISTIC procedure to generate deviance and Pearson chi-square for goodness of fit test.

Table 19. Multivariable Logistic Regression Analysis for Recurrent Infection at any time after the TOC visit (Population 3) (Secondary endpoint a)

	Odds ratio	95% CI	p -value
Arm 1 Standard Course(reference)			
Arm 2 Short Course			
Covariates			

Interaction Term			

SAS tips: SCALE=NONE in the MODEL statement of the PROC LOGISTIC procedure to generate deviance and Pearson chi-square for goodness of fit test.

Table 20. Multivariable Logistic Regression Analysis for Asymptomatic Bacteriuria at the TOC visit (Population 2) (Secondary endpoint b)

	Odds ratio	95% CI	p -value
Arm 1 Standard Course(reference)			
Arm 2 Short Course			
Covariates			

Interaction Term			

Table 21. Multivariable Logistic Regression Analysis for Symptoms that may be related to a UTI prior to or at the TOC visit (Population 2) (Secondary endpoint d)

	Odds ratio	95% CI	p -value
Arm 1 Standard Course(reference)			
Arm 2 Short Course			
Covariates			

Interaction Term			

Table 22. Multivariable Logistic Regression Analysis for positive urine cultures prior to or at the TOC visit (Population 2) (Secondary endpoint e)

	Odds ratio	95% CI	p-value
Arm 1 Standard Course(reference)			
Arm 2 Short Course			
Covariates			

Interaction Term			

Table 23. Multivariable Logistic Regression Analysis for Risk of emergent colonization with any antimicrobial resistant E. coli or K. pneumoniae in Gastrointestinal Tract (Population 4) (Secondary endpoint c)

	Odds ratio	95% CI	p-value
Arm 1 Standard Course(reference)			
Arm 2 Short Course			
Covariates			

Interaction Term			

Table 23 specifications: Repeat the analysis at enrollment visit, TOC visit, and outcome assessment visit separately as Table 26a, Table 26b, and Table 26c.

Table 24. Detailed listing for all adverse events possibly/probably related to study drug

Study Arm	Subject ID	Adverse event description	Onset date	Severity	Duration	Relationship to medication	Outcome

Table 24A. Adverse events possibly/probably related to study drug by body system and treatment arm (number of subjects)

	Arm 1: Standard Course Total= xxx N (%)	Arm 2: Short Course Total= xxx N (%)	
Total number of subject with adverse events			
Body as whole			

Table 24B. Adverse events possibly/probably related to study drug by body system and treatment arm (number of adverse events)

	Arm 1: Standard Course Total= xxx N (%)	Arm 2: Short Course Total= xxx N (%)	
Total number of adverse events			
Body as whole			

Table 25. Adverse events possibly/probably related to study drug by treatment arm

	Arm 1: Standard Course Total= xxx N (%)	Arm 2: Short Course Total= xxx N (%)	p -value
Total number of subjects with AEs			
Total number of Adverse events			
Number of AEs per patient			
0			
1			
2			
3+			
Severity of AE			
Mild			
Moderate			
Severe			
Serious adverse events			
Yes			
No			
Relationship to medication			
Related			
Not related			
Outcome			
Recovered/Resolved			
Unchanged			
Ongoing			
Yes			
No			

Specifications

- Restrict the analysis to population 1 separately by number of subjects with adverse event(s) (Table 24A) and number of adverse events (Table 24B).

The test for independence of AE among two arms can be obtained using Chi-square test (or Fisher test if any cell expected count is less than 5).

